Table of Contents

1.	LIST OF ABBREVIATIONS	4
2.	SYNOPSIS	5
3.	GENERAL INFORMATION AND ADMINISTRATIVE STRUCTURE	6
4.	PRODUCT INFORMATION	7
5.	RISKS AND BENEFITS	7
6.	INTRODUCTION	7
7.	CLINICAL INVESTIGATION DESIGN	7
8.	OBJECTIVE	8
9.	SELECTION OF CLINICAL INVESTIGATION POPULATION	8
10.	CLINICAL INVESTIGATION EVALUATIONS, PROCEDURES AND ASSESSMENTS	10
11.	STATISTICAL METHODS	12
12.	CLINICAL INVESTIGATION PLAN DEVIATIONS	18
13.	ADVERSE EVENTS/INCIDENTS	18
14.	REOPERATIONS	20
15.	ETHICS	20
16.	DATA COLLECTION PROCESS	21
17.	CLINICAL INVESTIGATION MONITORING	21
18.	DATA HANDLING AND RECORD KEEPING	21
19.	REPORTS	21
20.	PUBLIC REGISTRATION	21
21.	COMPLETION OF THE CLINICAL INVESTIGATION	21
22.	ESSENTIAL DOCUMENTS	22
23.	PUBLICATION POLICY	22
24.	REFERENCES	22
25.	CLINICAL INVESTIGATION PLAN SIGNATURE PAGE	24
26.	DOCUMENT VERSION HISTORY	25

1. List of Abbreviations

Acronym	Definition
ADE	Adverse Device Effect
AE	Adverse Event
CI	Confidence Interval
CIP	Clinical Investigation Plan
CRF	Case Report Form
eCRF	Electronic Case Report Form
EC	Ethics Committee
EDC	Electronic Data Capture
EUDAMED	European Database on Medical Device
ICF	Informed Consent Form
ICH-GCP	International Conference of Harmonisation Good Clinical Practice
IFU	Instructions for Use
ITT	Intent-to-Treat
Intra-Op	Intra-Operative
IRB	Institutional Review Board
LTFU	Lost to Follow-Up
MCS	SF-36 Mental Component Summary
MDD	Medical Device Directive
MDR	Medical Device Regulation
PCS	SF-36 Physical Component Summary
PP	Per Protocol
Pre-Op	Pre-Operative
SADE	Serious Adverse Device Effect
SAE	Serious Adverse Event
SAP	Statistical Analysis Plan
SF-36v2	36-Item Short Form Health Survey
UADE	Unanticipated Adverse Device Effect

2. Synopsis

Title	A Post-Market Clinical Evaluation of the Treatment of Tibia Fractures with the T2 Alpha Tibia Nailing System
Treatment	T2 Alpha Tibia Nailing System
Design	 Post-Market Multicenter Prospective Non-Randomized
Objective	The objective of this clinical investigation is to demonstrate the safety and efficacy/performance of the T2 Alpha Tibia Nailing System. Efficacy/performance of the procedure will be measured by an equal or higher (non-inferior)
	SF-36 Physical Component Summary (PCS) score result of the T2 Alpha Tibia Nailing System compared to the T2 Tibia benchmark literature (Wang, et al. 2017; Sanders, et al. 2014; Sun, et al. 2016; Chan, et al. 2016) at 12 months.
	In addition, demonstration of bone consolidation in correct alignment will be measured by Investigator assessment by 12 months.
	Safety of the T2 Alpha Tibia Nailing System will be demonstrated through reporting of device related intra-operative and post-operative Adverse Events/incidents by 12 months.
Target Population	Approximately 80 subjects are to be enrolled in this clinical investigation at up to 5 sites. Enrolled subjects will be assessed at Operative/Discharge, and at 3 Months, 6 Months and 12 Months after the index procedure.
Inclusion	a. Subject is a male or non-pregnant female age 18 years or older at the time of surgery;
Criteria	b. Subject is willing and able to give written informed consent and comply with the requirements of this Clinical Investigation Plan;
	c. Subject is intended to be treated with the Tibial Nail of the T2 Alpha Tibia Nailing System in accordance with the following legally cleared/approved Indications for Use:
	Indications for Use approved In United States and Canada include:
	 Open and closed tibial fractures Pseudoarthrosis and correction osteotomy
	 Pathologic fractures, impending pathologic fractures and tumor resections Fractures involving osteopenic and osteoporotic bone Nonunions and malunions
	Indications for Use approved In Europe and Other Countries include:
	 Open and closed tibial fractures Nonunions and malunions

543

Exclusion Subject has an active or suspected latent infection or marked local inflammation in or about the affected area Criteria Subject has compromised vascularity that would inhibit adequate blood supply to the fracture or the operative site Subject has documented bone stock compromised by disease, infection or prior implantation which cannot provide adequate support and / or fixation of the device d. Subject has documented or suspected sensitivity to materials Subject is obese such that he / she produces a load on the implant which can lead to e. failure of fixation of the device or to failure of the device itself f. Subject has inadequate tissue coverage over the operative site. Subject has implant utilization that would interfere with anatomical structures or g. physiological performance Subject has mental or neuromuscular disorder which would create an unacceptable risk h. of fixation failure or complications in post-operative care Subject has any other medical or surgical condition which would preclude the potential benefit of surgery **Endpoints Primary Endpoint** The primary endpoint of this clinical investigation is to confirm efficacy/performance at 12 months, as measured by the SF-36 Physical Component Summary (PCS). Confirmation of efficacy/performance at 12 months will be based on an equal or higher (non-inferior) SF-36 Physical Component Summary (PCS) result of the T2 Alpha Tibia Nailing System compared to the T2 Tibia benchmark literature (Wang, et al. 2017; Sanders, et al. 2014; Sun, et al. 2016; Chan, et al. 2016). Secondary Endpoints Safety: Incidence of device-related adverse events will be monitored by 12 months through data collection and analyses. Efficacy/Performance: Bone consolidation will be assessed by 12 months as

3. General Information and Administrative Structure

measured by Investigator assessment.

3.3. EDC SYSTEM

Name: IBM Clinical Development Email: [contact] [contact]

4. Product Information

All components of the T2 Alpha Tibia Nailing System were cleared and approved for sale and use prior to starting the clinical investigation. 510(k) clearance was received on 06Jun2018. This system is to be used only for indications for which it has been approved. Please see the approved Instructions for Use and Operative Technique manuals for a detailed description of the medical device(s) and instrumentation, and intended use information.

Medical device product traceability will be achieved by capturing the implant lot number.

5. Risks and Benefits

This prospective, multi-center, clinical investigation is designed to examine the safety and efficacy/performance of the T2 Alpha Tibia Nailing System, in accordance with the approved instructions for use, labeling and instrumentation. The potential risks to subjects are described in the approved Instructions for Use and Operative Technique manuals.

Potential benefits resulting from the T2 Alpha Tibia Nailing System over other devices and procedures, as demonstrated by superior scoring on outcome surveys and positive results on other clinical evaluation measurements (outlined in section 8), would also suggest affirmative clinical efficacy.

6. Introduction

The T2 Tibia Nailing System represented the latest and most comprehensive development of the original intramedullary principles presented by [name] in 1940. As an addition to the T2 Nailing System, Stryker has created a new generation tibial implant that offers an efficient treatment option for multiple indications. The T2 Alpha Tibia Nail includes new locking options and the ability to utilize the advanced locking screw which creates an axial and angular stable construct. New instrumentation offers a combination of innovation, simplicity and efficiency that is designed to suit the various needs of surgeons and OR staff.

7. Clinical Investigation Design

This investigation is a prospective, multicenter clinical investigation. It is anticipated that a total of 80 subjects will be enrolled at up to 5 sites. Enrollment is estimated to commence in Q4 of 2018. Neither

. .

subjects nor investigators are blinded to treatment and the clinical investigation includes a historical control which will be compared to the T2 Alpha Tibia Nailing System.

The enrollment period is expected to occur over 32 months. Total duration of enrollment, 12 month follow-up and analysis is expected to take 47 months. The clinical investigation has been designed to follow the surgeon's standard of care for tibia fractured subjects, in addition to a 12 month follow-up visit.

7.1. CLINICAL INVESTIGATION RATIONALE

The T2 Alpha Tibia Nailing System is fully integrated into the T2 Alpha Platform. The system includes two approaches: infrapatellar approach and suprapatellar approach and allows for multiple locking configurations for stable fixation. This clinical investigation will evaluate the safety and efficacy/performance of the T2 Alpha Tibia Nailing System.

8. Objective

8.1. PRIMARY ENDPOINT

The primary endpoint of this clinical investigation is to confirm efficacy/performance at 12 months, as measured by the SF-36 Physical Component Summary (PCS). Confirmation of efficacy/performance at 12 months will be based on an equal or higher (non-inferior) SF-36 Physical Component Summary (PCS) result of the T2 Alpha Tibia Nailing System compared to the benchmark literature (Wang, et al. 2017; Sanders, et al. 2014; Sun, et al. 2016; Chan, et al. 2016).

8.2. SECONDARY ENDPOINTS

- Safety: Incidence of device-related adverse events by 12 months will be monitored through collection and analyses.
- Efficacy/Performance: Bone consolidation will be assessed by 12 months as measured by Investigator assessment.

9. Selection of Clinical Investigation Population

Subjects participating in this clinical investigation will be recruited from the investigator's standard subject population, where all subjects presenting for treatment of tibial fractures will be evaluated for clinical investigation participation based on the eligibility criteria listed below.

9.1. INCLUSION CRITERIA

- a. Subject is a male or non-pregnant female age 18 years or older at the time of surgery;
- b. Subject is willing and able to give written informed consent and comply with the requirements of this Clinical Investigation Plan;
- c. Subject is intended to be, treated with the Tibial Nail of the T2 Alpha Tibia Nailing System in accordance with the following legally cleared/approved Indications for Use:

Indications for Use approved In United States and Canada include:

- Open and closed tibial fractures
- Pseudoarthrosis and correction osteotomy
- Pathologic fractures, impending pathologic fractures and tumor resections
- Fractures involving osteopenic and osteoporotic bone

.

Nonunions and malunions

Indications for Use approved In Europe and Other Countries include:

- Open and closed tibial fractures
- Nonunions and malunions

9.2. EXCLUSION CRITERIA

- a. Subject has an active or suspected latent infection or marked local inflammation in or about the affected area
- b. Subject has compromised vascularity that would inhibit adequate blood supply to the fracture or the operative site
- c. Subject has documented bone stock compromised by disease, infection or prior implantation which cannot provide adequate support and / or fixation of the device
- d. Subject has documented or suspected sensitivity to materials
- e. Subject is obese such that he / she produces a load on the implant which can lead to failure of fixation of the device or to failure of the device itself
- f. Subject has inadequate tissue coverage over the operative site.
- g. Subject has implant utilization that would interfere with anatomical structures or physiological performance
- h. Subject has mental or neuromuscular disorder which would create an unacceptable risk of fixation failure or complications in post-operative care
- i. Subject has any other medical or surgical condition which would preclude the potential benefit of surgery

9.3. WITHDRAWAL CRITERIA

If, during the clinical investigation, a subject must be prematurely withdrawn, the procedures outlined in this section must be followed. These procedures should not interfere with the initiation of any new treatments that are necessary to treat a subject's condition. Information on all withdrawn subjects will be documented.

Subjects may be withdrawn from the clinical investigation for any of the following reasons:

- a. Subject Withdrawal: A subject may voluntarily withdraw from the clinical investigation at any time and for any reason. The subject should be asked when possible, and without any form of coercion, the reason for his/her decision. If the participant withdraws from the clinical investigation completely, then data collected up until the point of withdrawal will be included in the final analysis. Subjects who decline to continue to take part will be given the opportunity to discuss/inform the research team of the reasoning behind their decision not to take part.
- b. Lost to Follow-Up (LTFU): A subject will be considered LTFU after all reasonable efforts have been made to contact the subject and request his/her continued participation in the clinical investigation. All attempts to contact the subject must be documented and should include at least two attempts to contact the subject by phone and one attempt via a certified letter. Data collected up until the point where the subject is LTFU will be included in the final analysis.
- c. Removal of Device or Adverse Event/Incident: The discontinuation of a subject's participation in the clinical investigation due to the removal of the Tibial Nail of the T2 Alpha Tibia Nailing System or Adverse Event/incident that prohibits his/her continued participation must be fully explained. All available information concerning the removal of the device or Adverse

Event/incident should be provided. Data collected up until the point of removal or Adverse Event/incident will be included in the final analysis.

- d. Death: The discontinuation of a subject's participation in the clinical investigation due to death must be fully explained. All available information concerning the death should be provided. Removal of a subject from continued follow-up in the clinical investigation due to death will not be considered a device failure unless the death is directly caused by, or attributable to, the T2 Tibia Nailing System. Data collected up until the point of death will be included in the final analysis.
- e. Other: A subject may be withdrawn by the Investigator if he/she believes that it is in the best interest of the subject or the IRB/EC may determine that a subject's continued participation in the clinical investigation represents an unacceptable risk to the subject. The Sponsor must be notified immediately if this occurs. All data collected up until the point of withdrawal or IRB/EC determination will be included in the final analysis.

A subject may also be withdrawn if the subject is non-compliant with the clinical investigation procedures or visits, or if a selection criteria violation is noted after the subject received the clinical investigation treatment and it is determined that the subject should be discontinued. All data collected up until the point of withdrawal will be included in the final analysis.

10. Clinical Investigation Evaluations, Procedures and Assessments

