10.5. SCHEDULE OF EVENTS

Assessment	Initial Assessment	3 Months a, b (+/-2 weeks)	6 Months a, b (+/-3 weeks)	12 Months ^b (+/-4 weeks)
Informed Consent	X ^c			
Demographics & Medical History	X			
Inclusion/Exclusion	X			
Primary Diagnosis	X			
Surgical Procedure	X			
Clinical Assessment of Bone Consolidation d, e		X	X	X
SF-36v2 (PCS & MCS)	X ^f	X	X g	X g
Subject Disposition h		X	X	X

Device-Related Adverse Events/Incidents & Reoperations will be collected throughout the course of the Clinical Investigation.

- a. Follow-up visit schedule to reflect Institutions' Standard of Care practices
- b. If the subject missed a visit and outside of visit window, every effort should be made to collect data instead of noting visit as missed. Visit windows are calculated from the index event, and not from the previous visit.
- c. Informed consent must be obtained prior to enrollment in the study (i.e., prior to performance of any study-related activities).
- d. Once bone consolidation is observed, assessment no longer needs to be conducted at the additional follow-up visits.
- e. Investigators should consider weight-bearing, pain and imaging when assessing bone consolidation.
- f. SF-36v2 evaluation must be collected post-informed consent.
- g. If bone consolidation is previously observed at the previous follow-up visit, evaluation is to be collected via phone.
- h. Subject Disposition assessment would occur at any time point for subject withdrawal prior to the completion of the clinical investigation.

0.00

11. Statistical Methods

The Statistical Analysis Plan (SAP) lists all variables/questions within this clinical investigation. Therefore, no additional "evaluation" chapter is required and needed for this CIP.

Data will be captured via IBM Merge EDC system and statistical analysis will be performed using IBM SPSS. All statistical hypotheses tests will be with confidence levels (1- α) of 95% and power (1- β) of 80%. The significance level (α) is 0.05 and the beta-value (β) is set to 0.20. Therefore, p-values \leq 0.05 will indicate statistical significance.

Results will be presented using summary tables and optionally supported by graphs. For detailed information per variable, see SAP.

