Chan et al.	SP	46.00	47.00	included
Sanders et al.	SP	40.80	46.00	included
Sun et.al.	SP	49.41	44.71	included
Sun et.al.	IP	43.21	43.81	included
Wang et.al.		79.10	77.00	excluded

Summary of explorative analysis is listed below:

18215 54 30

			Statistic	Std. Error
SF-36 PCS Physical at 12	Mean		43,4840	1,98495
months post-op	90% Confidence Interval	Lower Bound	39,2524	
	for Mean	Upper Bound	47,7156	
	Median		43,2100	
	Std. Deviation		4,43849	
	Minimum		38,00	
	Maximum		49,41	
	Range		11,41	
	Interquartile Range		8,31	
SF-36 PCS Mental at 12	Mean		45,7040	,63333
months post-op	90% Confidence Interval for Mean	Lower Bound	44,3538	
		Upper Bound	47,0542	
	Median		46,0000	
	Std. Deviation		1,41617	
	Minimum		43,81	
	Maximum		47,00	
	Range		3,19	
	Interquartile Range		2,74	

As the mean physical score (PCS) was slightly lower, it was used for the sample size calculation.

For the clinical investigation the one-sided 95% confidence interval will be applied.

Acceptance Criteria for Sample Size Calculation					
Significance Level (α)	0.05 (5%)				
Power (1-β)	0.80 (80%)				
Confidence Interval (CI)	0.95 (95%)				
Tails	1				
Path	Non-inferiority T2 Alpha Tibia (A) ≥ Benchmark (B, pooled benchmark results)				
Hamathagas Dain	Null (H ₀)	$A - B < -\theta$			
Hypotheses Pair	Alternative (H ₁)	$A - B \ge -\theta$			
Benchmark Timepoint	12 months post-operative				
Benchmark Mean	43.48 points SF-36 PCS at 12 months (IP an	d SP together)			
Benchmark Std. Dev.	No standard deviation results were given by Chan et al., Sanders et al. nor b Wang et al. Only Sun et al. reported standard deviations at 12 months postoperative for SF-36 PCS of 6.27 for the SP and of 6.52 for the IP subgroup As a worst-case, the double standard deviation reported by Sun et al. was used for the sample size calculation (2 * 6.52 = 13.04 points)				
Benchmark 90% CI of Mean	Lower 90% CI: 39.25 (two-sided 90% CI equals a one-sided 95% CI)				
Denchmark 90% CI of Mean	Upper 90% CI: 47.72				
Margin (-θ)	Lower 90% CI of Benchmark: 39.25				
Software Used	IBM SPSS Sample Power V3.0				

IBM SPSS Sample Power Output

One goal of the proposed clinical investigation is to test the null hypothesis that the population mean is 39.25. The criterion for significance (alpha) has been set at 0.050. The test is 1-tailed, which means that only an effect in the expected direction will be interpreted.

[figure not shown]

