With the proposed sample size of 61 subjects, the clinical investigation will have power of 80.0% to yield a statistically significant result.

This computation assumes that the population from which the sample will be drawn has a mean of 43.48 with a standard deviation of 13.04. The observed value will be tested against a theoretical value (constant) of 39.25.

This effect was selected as the smallest effect that would be important to detect, in the sense that any smaller effect would not be of clinical or substantive significance.

A second goal of this clinical investigation is to estimate the mean in the population. On average, a clinical investigation of this design would enable us to report the mean with a precision (95.0% confidence level) of plus/minus 2.77 points.

The precision estimated here is the median precision. Precision will vary as a function of the observed standard deviation (as well as sample size), and in any single clinical investigation will be narrower or wider than this estimate.

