11.3.2. Primary Analysis / Endpoint

This analysis is only part of the final report. The primary endpoint analysis will only be executed once at the end of the clinical investigation and will not be part of any interim or annual reports or presentations given in front of the final report.

The 12 months post-operative results for subjects implanted with the T2 Alpha Tibia Nailing System will be compared to Sanders et al: Semiextended intramedullary nailing of the tibia using a suprapatellar approach: radiographic results and clinical outcomes at a minimum of 12 months follow-up. J Orthop Trauma, 2014; Sun et al: The outcome comparison of the suprapatellar approach and infrapatellar approach for tibia intramedullary nailing. Int Orthop, 2016; and Chan et al: Suprapatellar Versus Infrapatellar Tibial Nail Insertion: A Prospective Randomized Control Pilot Study. J Orthop Trauma, 2016". Specifically, the SF-36 score results reported by Wang, et al. (2017), Sanders, et al. (2014), Sun, et al. (2016) and Chan, et al. (2016) will serve as the control groups for the T2 Alpha Tibia group.

Higher SF-36 PCS and MCS score results are linked to better subject results and vice versa.

The clinical investigation endpoint is non-inferiority to the control, meaning the clinical investigation result should be equal or better than the control. In this clinical investigation, an equal or better SF-36 score result means equal or greater (\geq). As only results from samples will be captured, results are mostly estimates of the true population parameter. These estimates vary by a certain area, where it is expected that the true population parameter falls within. Based on this, it is required to specify a lower limit for the acceptable difference or zone of indifference, denoted as $-\theta$.

Hypotheses were developed to allow for a comparison of the 12 months post-operative SF-36 PCS to evaluate effectiveness / performance. The 12 months post-operative SF-36 PCS is the primary endpoint of this clinical investigation. Hypothesis tests will be one-sided with a significance level α of 5%.

Hypothesis	Equations		Interpretation		
Null (H ₀) $A - B < -\theta$ $T2 \text{ Alpha Tibia (A)} - Co$ $pooled \text{ benchmark result}$		` '	Central tendency of A is inferior to the central tendency of B.		
Alternative (H ₁)	A – B ≥ -θ T2 Alpha Tibia (A) – 0 pooled benchmark res	,	Central tendency of A is non-inferior to the central tendency of B.		
95% H ₀ H ₁					

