4.6. MISSING DATA

The intent is to collect as complete a dataset as possible. Nevertheless, in some situations missing data cannot be avoided. The reports and tables therefore will show the number and percentage of missing cases for each analyzed variable in relation to the enrolled cases for each post-operative assessment.

Missing data will be reported for each variable or calculation (if any) and overall totals will be reported including the proportion of missing data (if any).

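### Subjects withdrawn after nail removal or a prohibiting adverse event can be absent from the 12-month PCS test, which may bias the mean upward, and no sensitivity analysis checks this

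*Protocol*

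**What the plan says.** Protocol 9.3 lists reasons for which a subject may be withdrawn. Item (c) covers discontinuation "due to the removal of the Tibial Nail of the T2 Alpha Tibia Nailing System", or an adverse event/incident of a kind that rules out continued participation. Data gathered up to the removal or event enter the final analysis. Nothing asks for a 12-month SF-36 afterwards.

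The primary analysis (Protocol 11.3.2; SAP 3.1.1 and 6.6) is a one-sample t-test, or a sign test if normality fails, on the 12-month PCS. Protocol 11.1 says: "The observed value will be tested against a theoretical value (constant) of 39.25".

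On missing data, SAP 4.6 says: "The reports and tables therefore will show the number and percentage of missing cases for each analyzed variable". Protocol 11.4 says the same. Neither document contains an imputation rule, a failure rule or a sensitivity analysis for the primary endpoint.

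ITT is all enrolled subjects and PP is ITT without major violations (Protocol 11.2; SAP 5.1). Neither definition says what happens to a subject with no 12-month PCS.

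Footnote g of the schedule (Protocol 10.5; SAP 4.4) provides that the SF-36 "evaluation is to be collected via phone", but only where bone consolidation was already seen at the preceding visit.

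**The concern.** A subject without a 12-month PCS contributes nothing to a one-sample test of that score. Keeping the earlier data does not bring the subject back in. For the primary test, ITT and PP are therefore both available-case analyses, and comparing them cannot reveal a problem caused by who is missing.

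The subjects at issue are not a random subset. The named reoperation reasons in SAP 6.1 include non-union, infection, implant failure and pain, and Protocol 14 counts implant removal as a reoperation. Such subjects would plausibly score low on a physical-function scale. If they leave, the observed mean rises. The comparator is a fixed constant, so no concurrent arm exists in which similar losses could offset the shift. At stake is a non-inferiority finding that owes something to poor outcomes leaving the data set.

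**Working it through.** **Inputs from the documents**
- Test: "Hypothesis tests will be one-sided with a significance level α of 5" per cent (Protocol 11.3.2), against 39.25.
- Planning assumption: the population "has a mean of 43.48 with a standard deviation of 13.04" (Protocol 11.1).
- Margin: 43.48 − 39.25 = 4.23 points.
- Origin of the SD: a doubled literature value, "used for the sample size calculation (2 * 6.52 = 13.04 points".
- Enrolment: 80 (74 rounded up), with 20% expected drop-out (SAP 3.2).

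**Inputs assumed, because the documents give neither**
- k, the number withdrawn under 9.3(c) with no 12-month PCS.
- gap, the mean PCS of those analysed minus the unobserved 12-month mean of those withdrawn.

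**Step 1: reproduce the plan's figure.** Protocol 11.1 states: "With the proposed sample size of 61 subjects, the clinical investigation will have power of 80.0% to yield a statistically significant result". With n = 61, the noncentrality is 4.23 × √61 / 13.04 = 2.53, and the one-sided noncentral-t power is 0.805, the value in the SAP output. At n = 60 it is 0.799, so 61 is the smallest n that reaches 80%. The figure reproduces.

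**Step 2: what the drop-out allowance covers.** 80 × 0.8 = 64 analysable subjects, power 0.822. The allowance protects precision. It does nothing about losses related to outcome.

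**Step 3: bias.** Analysed mean − full-cohort mean = (k/80) × gap.

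**Step 4: error rate.** Set the full-cohort mean at exactly 39.25, so that the nominal one-sided error is 5%. The analysed n is 80 − k and the noncentrality is bias × √(80 − k) / SD. The error is the probability that the noncentral t exceeds the 5% critical value on 80 − k − 1 degrees of freedom. Example with k = 8 and gap = 10: bias = 0.1 × 10 = 1.0; noncentrality = 1.0 × √72 / 13.04 = 0.65; error = 15.9%.

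| Withdrawn (k) | Gap (points) | Bias (points) | Share of 4.23 margin | Error, SD 13.04 | Error, SD 6.52 |
|---|---|---|---|---|---|
| 2 | 5 to 15 | 0.13 to 0.38 | 3% to 9% | 5.9% to 8.2% | 7.0% to 12.7% |
| 4 | 5 to 15 | 0.25 to 0.75 | 6% to 18% | 7.0% to 12.5% | 9.4% to 25.7% |
| 8 | 5 to 15 | 0.5 to 1.5 | 12% to 35% | 9.3% to 24.9% | 15.9% to 61.4% |
| 16 (upper bound) | 5 to 15 | 1.0 to 3.0 | 24% to 71% | 15.0% to 57.0% | 33.3% to 97.7% |

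The 16-subject row is the plan's whole 20% all-cause allowance. It is an upper bound, not an estimate of withdrawals for removal or adverse events.

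**Step 5: the reverse case.** If those withdrawn would have scored 5 points better, the bias is −0.25 points for k = 4 and −0.5 points for k = 8. At SD 13.04 the error falls to 3.5% and 2.5%.

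**Step 6: with the scores collected.** If every such subject supplies a 12-month PCS, k = 0 for this mechanism, the bias term is zero and the error returns to 5%.

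**The case against.** Several points on the other side stand.

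- A reader might infer that any nail removal or device-related event ends participation. The text does not say so: withdrawal is permissive, and the adverse event must be one that rules out staying in. Reoperations, including implant removal, are recorded throughout (Protocol 14), and the time-to-reoperation analysis allows for several in one subject (Protocol 11.3.4), so some of these subjects are expected to remain.
- A reader might infer that the plan is shown to inflate the mean. It is not. No document reports PCS after removal, the reoperation form has an open category for other reasons, and removal in a healed subject doing well would lower the analysed mean.
- A reader might take the 20% drop-out as the relevant rate. It is an all-cause figure that the plan calls worst case, taken from a lost-to-follow-up rate.
- The documents do not say how the benchmark studies treated such subjects, so bias relative to the benchmark cannot be judged.
- Failures remain visible elsewhere: withdrawals are tabulated by site, visit and reason (SAP 5.3), reoperation reasons are reported (SAP 6.1), and time to first device-related event is analysed (SAP 6.6).

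None of this closes the gap. The instruction to make every effort to collect data (Protocol 10.4 and schedule footnote b) concerns missed visits, and the contact attempts in 9.3(b) concern loss to follow-up; neither covers a subject whose participation has been ended. Reporting failures in other tables does not return them to the primary test. Uncertainty about direction and number is the reason to prespecify a sensitivity analysis.

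**Conclusion.** The point holds as a possible bias, not a demonstrated one. The plan permits withdrawal after nail removal or a prohibiting adverse event, stops data there, tests observed 12-month PCS against a constant and has no rule for missing scores. If those withdrawn would have scored lower, as the named reoperation reasons suggest, the test leans toward non-inferiority.

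The size rests on assumed numbers and deficits. For 2 to 8 withdrawals the effect runs from negligible to material, and even 8 subjects with a 15-point deficit move the mean by about a third of the margin. The error rates further assume an SD of 13.04 among those analysed and the t-test form of the primary analysis; at the undoubled SD of 6.52 the same shifts matter more. This is a worthwhile, inexpensive improvement rather than a flaw that invalidates the design.

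**What to change.** 1. **Protocol 9.3(c) and schedule footnote g.** State that nail removal or an adverse event/incident does not by itself end collection of the 12-month SF-36 unless the subject withdraws consent. Widen footnote g, which now allows phone collection only after consolidation has been observed, so that it covers these subjects. Make the same footnote change in SAP 4.4. This concerns data collection only, not clinical management.

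2. **SAP 4.6 and 6.6.** Add a tipping-point sensitivity analysis for ITT subjects without a 12-month PCS. Impute them around the observed mean, lower the imputed values in steps until the one-sided p exceeds 0.05, and report that shift so that readers can judge whether it is plausible. Report deaths separately. If the sign test is used, count all missing subjects as below 39.25 as the extreme case.

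The cost is a few extra contacts, a short protocol and SAP edit, and one extra table.
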